Treating Cynophobia with Augmented Reality Exposure Therapy

[NCT ID not yet assigned]

11.04.2022

1. Call for Participation

A call for participation in the study will be made via social media platforms. Volunteers who would like to participate will be able to click on a link and register to the study if they agree to be contacted by the research team.

2. Administration of Specific Phobia Scale

The Turkish version of the Specific Phobia Scale will be administered to the volunteers of the study after they are explained the study and after they give their informed consent. They will be instructed to fill the questionnaire regarding their dog phobia. They will also be asked to fill a demographic form. Those who score above the cut-off point will be invited to the clinical and diagnostic interviews.

3. Clinical Interviews

During the clinical interviews, a clinical psychologist will interview volunteers regarding their phobia symptoms in accordance with DSM-5 criteria. With those volunteers who have a clinician confirmed phobia, a second interview will be conducted using Structured Clinical Interview for DSM-5 Disorders (SCID) to see if they have a mental disorder such as psychosis, substance use disorder, or epilepsy. Those participants who will be included in the study will be contacted and invited to the laboratory.

4. Explanation of the Principles and Obtaining the Informed Consent

Both groups will be invited to the laboratory for the baseline measurement. Upon their arrival, the study will be explained to them and why it is necessary to have a baseline measure of their phobia severity by seeing a real dog. The briefing and explanation will follow above-given 3 paragraphs:

We explain to the participants that their phobia is just illogical, not meaningless. It has been acquired through some form of learning. There are different ways of learning. People may learn socially, by talking to people or just observing them. People learn also through experience. We explain that for whatever reason the participant's brain has associated dogs with danger. The exposure we will be doing works in a similar way that parents hold their kid's hand and open the closet to show them there is no monster under the hood.

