We have to do the same to our brain. It has to unlearn the previous learning that dogs are dangerous. In other words, the brain has to learn by experience that its feared object is actually safe by spending safe time with it. That's the basic principle of exposure therapy. We gradually expose a person to what they're afraid of until the brain gradually learns it's

safe and the fear goes away. We also explain that exposure therapies are very effective. By conducting it with AR, we offer our participants the feeling of safety by exposing them to a virtual dog. By means of this technology, our participants will feel a sense of total control in terms of what is going to happen. Even though they will know that the dogs are not real, the brain does not distinguish the experience in terms of learning.

After the briefing, both groups will be given a form of informed consent. After that the baseline measurements with the real dog will be taken. The participants will then be randomly assigned to either control or intervention conditions. Both groups will be informed about their groups, explained the rationale for the random assignment and control group. The control group will only be tested for baseline where the intervention group will receive Augmented Reality Exposure Therapy.

5. Real Dog Exposure to Measure the Baseline

We explain to the patients why we need to measure their progress with the real dog. To have a baseline measure of their phobia, we introduce the dog to the patient. When the patients stand 7 meters away from the real dog we encourage them to walk closer by saying "Is that it or do you think you can approach more?". If they can go closer to the dog, we say "Can you hold your hand close to it? Can you touch it?" When the participants reach the limits of their comfort zone that is they can not approach closer, we ask whether they would like to finish the testing.

The distance participants can approach the dog will be measured in terms of meters, the Behavioral Approach Test (BAT). Any physical contact with the dog will be measured visually for exclusion criteria i.e., the participants who can touch the dog will be excluded from the study based on the reasoning that they do not have a real phobia.

The Skin Conductance Response (SCR) will be measured to see physiological stress of the individuals via Shimmer3 GSR+ device placed on one finger. At the same time, participants will report how stressed they are (subjective unit of distress, SUD).

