- We leave the room and talk with the patient via the walky talky.
- We say "I will put these 3 dogs and they are going to move all around you without my prompt."
- We include their cognitive processing and encourage them to describe the dogs by saying "Tell me what the dogs are doing? Tell me how many dogs are you counting? How many of them are moving, how many of them are standing or jumping?"
- When the participants are comfortable with their virtual phobic stimuli (SUD = 2) or their SUD's did not change for the last 10 minutes, we finish the intervention.

Ending

- When it's finished, we say "That is how exposure therapy works."
- We encourage them to try it at home. We say: "Watch videos and look at pictures of dogs. If you see a dog and you know it is safe, try to pet and play with them. If you see a dog on a leash walking with their owner, walk by them. Don't avoid it."
- Finally, we ask them to come back for the next measurement.

8. Follow-Ups

- At 1 week and 1 month follow-ups, we contact the participants and invite them to the lab. We test them using the real dog to confirm if their gains are maintained. We use the same measures and protocol as the 6th step, Real Dog.

9. Statistical Analysis

Data will be analyzed by using a statistical software called IBM SPSS 26.0. Considering the groups as fixed factor, linear mixed models will be used to evaluate the effectiveness of the Augmented Reality Exposure Therapy on the primary (Behavioral Approach Task) and secondary outcome measures (Specific Phobia Scale, Skin Conductance and Subjective Units of Distress).

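### The Specific Phobia Scale is a secondary effectiveness outcome, but the plan schedules it only at screening, before randomisation

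*Combined protocol and SAP*

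**What the plan says.** - **Role of the scale.** Section 9 assesses the therapy with linear mixed models, group being the fixed factor. The primary outcome is the behavioural approach task, and there are three "secondary outcome measures (Specific Phobia Scale, Skin Conductance and Subjective Units of Distress").
- **When it is given.** Section 2: "The Turkish version of the Specific Phobia Scale will be administered to the volunteers of the study". The score then decides who goes further: "Those who score above the cut-off point will be invited to the clinical and diagnostic interviews".
- **What is measured at the laboratory baseline.** Section 4, after consent: "After that the baseline measurements with the real dog will be taken". Random assignment follows. Section 5 describes that test and names three measures. Distance "will be measured in terms of meters, the Behavioral Approach Test (BAT"); "The Skin Conductance Response (SCR) will be measured to see physiological stress"; and "participants will report how stressed they are (subjective unit of distress, SUD").
- **What is measured later.** Section 8 brings participants back at 1 week and 1 month for a real-dog test. It takes the measures from a sixth step that it calls Real Dog. Section 6 in the current numbering describes the rooms; the real-dog test is section 5.
- **Control group.** Section 4 adds: "The control group will only be tested for baseline". Section 8 invites participants without naming a group.

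**The concern.** An outcome used to judge effectiveness has to be observed after treatment has had a chance to act. For the scale, the plan describes no such observation, so sections 8 and 9 conflict: one sets follow-up measures that leave the scale out, and the other analyses it as an outcome.

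The scale is also the only listed outcome not taken during the encounter with the laboratory dog. SUD would remain as a self-report measure, but it comes from that same encounter. If staff repeat the scale on their own initiative, nothing settles at which visits, in which groups, or whether before or after the dog test. A score that is not collected at a visit cannot be recovered later.

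**Working it through.** The plan gives no sample size, power or error rate, and none is needed. The check is a count of scheduled measurements followed by one expectation.

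**1. Where the scale is named.** It appears three times: the section 2 heading, the section 2 text and section 9. It does not appear in sections 3 to 8, which cover the interviews, baseline, intervention and follow-up.

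**2. Order of events.** Scale at screening (section 2), interviews (section 3), real-dog baseline, then randomisation (sections 4 and 5), intervention (section 7), follow-up (section 8). The one scale score precedes randomisation.

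**3. Outcomes covered by the follow-up rule.** Section 9 lists 1 primary + 3 secondary = 4 outcomes. The real-dog step names 3 of them, so 4 − 3 = 1 outcome, the scale, falls outside the rule.

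**4. Scheduled administrations.** This reads section 8's sixth step as section 5. SUD ratings during the augmented reality session are not counted, because only the intervention group has them.

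| Outcome | Before randomisation | After randomisation |
|---|---|---|
| Behavioural approach (primary) | 1 | 2 (1 week, 1 month) |
| Skin conductance | 1 | 2 |
| SUD at the real-dog test | 1 | 2 |
| Specific Phobia Scale | 1 (screening) | 0 |

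**5. Sensitivity to a missing step.** A line at the end of section 5 addresses a participant who is already comfortable with the dogs, which suits a test after treatment. If it marks a lost post-treatment test, the first three rows become 1 / (2 + 1) = 1 / 3. The scale stays at 1 / 0 unless that unseen step included it.

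**6. What the model could estimate.** Let S be the screening score and Z the assigned group. Assignment is random and made after S is recorded, so E[S | Z = intervention] − E[S | Z = control] = 0 for any size of treatment effect. A group term fitted to S therefore describes chance imbalance at entry. With one record per participant there is also no change over time to model. If a participant random intercept were fitted (section 9 does not say), it could not be separated from residual error.

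**7. The separate control-group sentence.** Read literally, section 4 gives controls 0 post-randomisation values on 4 of 4 outcomes. This is a different defect, and scheduling the scale would not cure it.

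**The case against.** The best reply is that this is an incomplete visit schedule. Listing the scale as an outcome implies that it will be repeated, and section 8 says that the real-dog measures are used without saying that nothing else is. No step has both the number and the name that section 8 cites. Together with the stray line in section 5, this suggests that a post-treatment step is missing from the text, and it could have included the scale. The closing instruction of the intervention also asks participants back for a further measurement without naming an instrument.

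Much of this is fair. Repetition probably was intended, and the missing step cannot be ruled out. The 1 / 2 count for the other outcomes also depends on repairing a faulty cross-reference and on setting aside the literal control-group sentence, which has a milder reading as a contrast between being tested and being treated. None of this supplies a scheduled scale score after randomisation. Section 8 does define the follow-up measures, and the only real-dog step available leaves the scale out. Intent does not fix the visits, the groups or the point in the visit.

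A further objection is that the screening score is a poor baseline because it was used for selection. Change within a group from that score is open to regression to the mean. The cut-off is applied to everyone before randomisation, however, so the comparison between groups remains valid if both groups complete the scale later.

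**Conclusion.** The concern holds. As written, the plan has one scale score per participant, taken before randomisation, and so no estimable treatment effect on an outcome listed for effectiveness. Confidence in the reading of the text is high. The conclusion is about what the current text schedules, not about what the sponsor intended, and it takes section 5 as the step that section 8 means.

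The reach is limited to 1 of 4 outcomes (1 of 3 secondary, with no ranking among them). The primary outcome is not affected by this point. It should be corrected, but by itself it does not undermine the trial. The control-group sentence has wider consequences and should be judged on its own; it adds nothing to the weight of this point.

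**What to change.** - **Section 8.** Correct the reference to the sixth step and list the follow-up measures by name. Add the Specific Phobia Scale at 1 week and 1 month in both groups, at one fixed point in the visit relative to the dog test. State that the screening score is its baseline and that the treatment effect is the difference between groups, not change within a group.
- **Post-treatment test.** If there is one, describe it and say whether the scale is given there.
- **Alternative.** If the scale will not be repeated, remove it from the secondary outcomes in section 9 and call it a screening tool.
- **Separately.** Reconcile section 4's control-group sentence with section 8, so that control follow-up is explicit for every outcome.

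Cost of keeping the scale: two extra questionnaires per participant at visits already described (the plan does not give the completion time), plus edits to sections 4 and 8. If control visits are not already planned, two per control participant are needed, but the other three outcomes need them too. Cost of removing it: one edit to section 9 and the loss of one of three secondary outcomes.
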